#### 17.1. DERIVATIONS

Compliance to study treatment is based on the Drug Accountability eCRF and will be calculated as the number of capsules/tablets taken (total dispensed – total returned) divided

by the prescribed number of capsules/tablets, expressed as a percentage (see calculations below).

The study treatment is given three times daily (tid), and it is assumed that the subject should take study treatment from the morning of the visit day at which their treatment is initially dispensed to the evening before their last treatment return date, as subjects are advised to wait to take their dose at the study site until all assessments and procedures have been completed on study days. For example, if the initial dispensation date is Day 1 and the last return date is Day 85, then the subject should have taken 3 capsules/tablets each day on Days 1 to 84; hence, the total number of prescribed capsules would be  $84 \times 3 = 252$ . Multiple bottles may be dispensed at one visit; in these cases, "Per Visit" compliance will be nonmissing if at least one bottle is returned.

• "Per Visit" Compliance to study treatment at Visit X will be calculated as follows:

```
\frac{([\text{N of Capsules dispensed at Visit }(X)] - [\text{N of Capsules returned at Visit }X+1])}{\{[\text{Date of Visit }X+1] - [\text{Date of Dispensing at Visit }(X)]\} \times 3} \times 100
```

• Overall Compliance to study treatment will be calculated as follows:

For subjects who permanently stop the study treatment before Week 12, the "Date of Visit X" in Overall Compliance calculations will be replaced by the date of study withdrawal.

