#### 4.2.2. Exclusion Criteria

Subjects are excluded from the LTE if they meet any of the following exclusion criteria:

- 1. Subject meets any exclusion criteria from the Main Study at the time of assessing eligibility for the LTE, unless approved by the Sponsor in advance.
- 2. Subject had less than 75% overall compliance with eDiary entries during the Main Study.
- 3. Subject deviated from the prescribed dosage regimen during the Main Study (ie, overall study treatment compliance less than 85% or more than 115%), unless approved by the Sponsor in advance.

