#### 5. STUDY TREATMENT

Olorinab (APD371) is a highly selective, full agonist of CB2.

Olorinab drug substance, drug product (capsules and tablets), and matching placebo (capsules and tablets) are manufactured in compliance with current Good Manufacturing Practices. Capsules and tablets are packaged in the following configuration: 63 count in 100-cc high-density polyethylene (HDPE) bottles heat-induction sealed with child-resistant screw cap. Bottles will be labeled in compliance with local country requirements and shipped to participating clinical study sites for study use.

Although 2 different dosage forms (capsules and tablets) of study treatment will be used in this study, individual subjects will remain on the same dosage form assigned at the time of randomization throughout the Main Study Treatment Period. During the LTE, all subjects will receive the tablet dosage form, regardless of which dosage form they were assigned to during the Main Study.

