#### **6.4.** PER PROTOCOL SET

The Per Protocol set will include all subjects in the FAS without major protocol violations that might affect the evaluation of the effect of the study treatment on the primary endpoint. These protocol violations may include not meeting key inclusion/exclusion criteria, gross treatment non-compliance, receiving incorrect treatment, treatment unblinding by the investigator, or concomitant use of protocol-prohibited medications. The final determination on protocol violations, and thereby the composition of the Per Protocol set will be made prior to database lock of the Main Study and will be separately documented. Subjects will be summarized by treatment to which they were randomized, regardless of treatment actually received. If subjects are randomized but not treated, they will be excluded from Per Protocol set.

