#### 16.1. DERIVATIONS

Compliance to study treatment is based on the Drug Accountability eCRF and will be calculated as the number of capsules/tablets taken (total dispensed – total returned) divided by the prescribed number of capsules/tablets, expressed as a percentage (see calculations below).

The study treatment is given three times daily (tid), and it is assumed that the subject should take study treatment from the morning of the visit day at which their treatment is initially dispensed to the evening before their last treatment return date, as subjects are advised to wait to take their dose at the study site until all assessments and procedures have been completed on study days. For example, if the initial dispensation date is Day 1 and the last return date is Day 387, then the subject should have taken 3 capsules/tablets each day on

Days 1 to 386; hence, the total number of prescribed capsules would be  $386 \times 3 = 1,158$ . Multiple bottles may be dispensed at one visit; in these cases, "Per Visit" compliance will be non-missing if at least one bottle is returned.

• "Per Visit" Compliance to study treatment at Visit X will be calculated as follows:

```
\frac{([\text{N of Tablets dispensed at Visit }(X)] - [\text{N of Tablets returned at Visit }(X+1)])}{\{[\text{Date of Visit }(X+1)] - [\text{Date of Dispensing at Visit }(X)]\} \times 3} \times 100
```

• Overall Compliance to study treatment will be calculated as follows:

```
{([N of Tablets dispensed at Visit 1] - [N of Tablets returned at Visit 2])
+ ···+

([N of Tablets dispensed at Visit (X-1)] - [N of Tablets returned at Visit X])}

[Date of Visit X] - [Date of Dispensing at Visit 1] ×3
```

For subjects who permanently stop the study treatment before Week 52, the "Date of Visit X" in Overall Compliance calculations will be replaced by the date of study withdrawal.

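### The compliance formula counts the contents of an unreturned bottle as taken whenever another bottle from the same visit comes back, which distorts the by-visit and overall compliance tables

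*SAP*

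**What the plan says.** Main Study SAP 17.1 names one data source: "Compliance to study treatment is based on the Drug Accountability eCRF". Its numerator is the "number of capsules/tablets taken (total dispensed – total returned) divided" by the number prescribed. The printed per-visit formula subtracts units returned at the next visit from all units dispensed at the current one. For visits with more than one bottle, the value "compliance will be nonmissing if at least one bottle is returned".

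LTE SAP 16.1 has the same definition and the same rule ("compliance will be non-missing if at least one bottle is returned"). It also prints an overall formula that sums the same differences across visits. The corresponding Main Study overall formula is not visible in the available text.

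Main Study SAP 17 reports overall compliance in three categories (below 85%, 85% to 115%, above 115%) and also summarises compliance by visit. Protocol 5.6 applies the 85% to 115% band at each of Main Study Visits 4 to 8 as a trigger for counselling. It asks for a reason when compliance exceeds 115% or when nothing at all is returned.

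**The concern.** The rule treats the same unknown in two ways. If no bottle comes back, per-visit compliance is by implication missing, which accepts that the fate of the contents is not known. If one of two bottles comes back, the contents of the other become doses taken. No text limits the numerator to returned bottles, and the calculation does not use the eDiary dosing record.

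The error runs upward only, but it misleads in two directions. Low intake can be reported inside the 85% to 115% band, and full intake can be reported as overdosing. At stake are the by-visit and overall compliance results by dose. Two other uses may be affected if they draw on this calculation: the Per Protocol judgement on "gross treatment non-compliance" (Main Study SAP 6.4) and the LTE exclusion for "overall study treatment compliance less than 85% or more than 115"% (protocol 4.2.2).

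**Working it through.** **Inputs**
- Units per day: 3. Main Study SAP 17.1 says "the subject should have taken 3 capsules/tablets each day on Days 1 to 84".
- Units per bottle: 63. Protocol 5 describes "63 count in 100-cc high-density polyethylene (HDPE) bottles".
- Interval: Week 4 to Week 8 is 28 days (visit list in Main Study SAP 9.1). The other treatment intervals are 14 days.
- Assumption: two bottles (126 units) are dispensed at Week 4. The interval needs 28 × 3 = 84 units, more than one bottle holds, so two is the minimum if that visit supplies the whole interval. A 14-day interval needs 42 units, which one bottle covers.

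**The plan's own figure.** Prescribed units for Days 1 to 84: 84 × 3 = 252. Reproduced.

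**Per visit, Week 4 to Week 8.** Compliance = (dispensed − returned) / (days × 3).
- One-third taker: takes 28 units from one bottle, returns it with 35 left, and leaves the other untouched at home. Reported: (126 − 35)/84 = 91/84 = 108.3%. True: 28/84 = 33.3%.
- In this scenario the reported value is (63 + units taken)/84. It lies inside the band for 9 units (72/84 = 85.7%) up to 33 units (96/84 = 114.3%), a true intake of 10.7% to 39.3%.
- Perfect taker: empties and returns one bottle, takes 21 from the other and leaves it at home with 42 in it. Reported: 126/84 = 150%. True: 84/84 = 100%.
- Visit timing matters. With true intake of one third, a 31-day interval gives (31 + 63)/93 = 101.1%, but a 25-day interval gives (25 + 63)/75 = 117.3%, which is above the band.

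**Overall, Main Study.** This applies the SAP's general definition, with 252 units prescribed and everything else returned.
- Each lost full bottle adds 63/252 = 25.0 points.
- One lost full bottle: reaching 85% needs a true intake of at least 152 units, since (152 + 63)/252 = 85.3% and (151 + 63)/252 = 84.9%. True compliance is then 152/252 = 60.3%.
- Perfect taker with one unreturned bottle holding 42: (252 + 42)/252 = 294/252 = 116.7%.
- One-third taker (84 units): one lost full bottle gives 147/252 = 58.3%, two give 210/252 = 83.3%, three give 273/252 = 108.3%.

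**LTE illustration.** Assume an 8-week interval with three bottles (189 dispensed, 168 needed). A subject who took 20 and returned only one bottle, with 43 left, is reported at (189 − 43)/168 = 86.9%. True: 20/168 = 11.9%. This needs two bottles left at home.

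**The case against.** The arithmetic is not in dispute, but several stronger readings are tempting and the documents do not support them.

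- **A subject who takes a third of the dose will be classed as compliant.** That is a result for one visit. The SAP 17 categories and the LTE criterion use overall compliance, where one lost full bottle leaves that subject at 58.3% and two at 83.3%.
- **Partial returns inside the band are never queried.** Protocol 5.6 has returns counted at each visit and bases compliance on accountability, open questioning of the subject and eDiary review. Only the specific request for a reason is limited to values above 115% or no return. Sites may catch some cases, and the 150% case prompts that request, with the response listed. But the SAP calculation uses neither the questioning nor the eDiary, and no rule corrects the number.
- **The formula decides LTE entry and Per Protocol membership.** No text says so. The LTE criterion stands in Amendment 3.0 (February 2020), the Main Study SAP is dated January 2021, and the sponsor may approve exceptions. SAP 6.4 gives no numerical cutoff for non-compliance. These effects are possible, not shown.
- **A null efficacy result would be misread as lack of effect.** The primary analysis uses the Full Analysis Set and ignores compliance. Intake is also informed by missed doses and interruptions (SAP 16) and trough concentrations at Weeks 2, 4, 8, 10 and 12 (SAP 20.2).

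It also stands that the documents give no frequency of unreturned bottles, and that little turns on the LTE. The LTE SAP has no formal comparisons and no Per Protocol set, and the extension was ended early.

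**Conclusion.** The point holds as a defect in a stated rule. Under the formulas as written, the contents of an unreturned bottle enter the numerator as doses taken once another bottle from that visit is returned. For the Week 4 to Week 8 visit the error can move 33% to 108%, or 100% to 150%. Overall, one lost full bottle adds 25 points, enough to bring a true 60% up to 85%, and a perfect taker who loses a bottle holding 42 shows 116.7%.

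The sizes rest on two assumptions: two bottles at Week 4, and an overall Main Study formula that follows the SAP's general definition. How many subjects would be affected cannot be judged from the documents. The established effect is on the by-visit and overall compliance tables. An effect on the Per Protocol set or LTE eligibility depends on whether those decisions use this calculation. The primary efficacy analysis is unaffected.

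**What to change.** In Main Study SAP 17.1 and LTE SAP 16.1:
- Treat an interval as missing for the pill count unless every bottle dispensed for it is accounted for.
- Drop both the units and the days of such an interval from the overall ratio, so that numerator and denominator cover the same time.
- Report the number of affected intervals by arm.
- Use the eDiary dosing record as a cross-check, or as a substitute, only if the item captures how many doses were taken. Protocol 5.6 has it completed once a day for a drug taken three times a day, and the item itself is not visible.

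If the intention was to count only returned bottles, the SAP should say so and define the matching denominator.

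The cost is SAP wording and programming. The downside is that some subject-intervals become missing. Subjects who fail to return bottles may differ in intake from those who do, which is why the count by arm belongs beside the table.

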## 3.10. Early Termination Visit

Subjects who stop taking study treatment prior to the end of the Main Study Treatment Period will return to the clinic for a Main Study Early Termination Visit. Subjects enrolled in the LTE who stop taking olorinab prior to the end of the LTE Treatment Period will return to the clinic for an LTE Early Termination Visit. Early Termination Visit assessments are detailed in the Every effort should be made to schedule Early Termination procedures within 3 days of the last dose of study treatment and before initiation of any new treatments which could affect endpoints. After completion of the Early Termination Visit, subjects should also return (when possible) for a Follow-Up Visit approximately 2 weeks (± 3 days [for the Main Study] or ± 7 days [for the LTE]) after discontinuation of study treatment. Site staff will work with subjects who withdraw early to obtain as much follow-up

data as possible.

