## **5.6.** Study Treatment Compliance

Study treatment will be dispensed at the study visits scheduled in the

Subjects will document study treatment administration once daily in the subject eDiary. At Visit 3, subjects will be instructed on how to record treatment administration in the subject eDiary.

Starting with Visit 4, subjects will be instructed to bring unused study treatment and used study treatment packaging to each study visit to assess compliance with study treatment administration. Returned study treatment should be counted at each visit. Compliance with the scheduled dose should be assessed based on the following:

- Study treatment accountability
- Non-directed verbal questioning
- Review of eDiary responses regarding study treatment administration

Deviation(s) from the prescribed dosage regimen will be recorded in the eCRF. If compliance is not between 85% and 115%, inclusive, at Main Study Visits 4 through 8 or LTE Visits 3 through 7, the subject will be counseled by the Investigator or designee about the importance of compliance with the regimen.

Subjects with administration compliance greater than 115% and subjects who do not return any study treatment or study treatment packaging will be asked for the reason for the overcompliance or missing study treatment and their response will be recorded in the eCRF.

The Sponsor retains the right to require the withdrawal of any subject who violates the protocol.

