# 6. DISCONTINUATION OF STUDY TREATMENT AND SUBJECT DISCONTINUATION/WITHDRAWAL

## **6.1.** Discontinuation of Study Treatment

A subject's study treatment may be discontinued early for any of the following reasons:

- AE
- Withdrawal by subject
- Investigator decision
- Study termination by Sponsor (the study may be terminated early if, in the opinion of the Sponsor, Medical Monitor, data safety monitoring board (DSMB), Investigator, or Institutional Review Board [IRB] an unacceptable risk to the safety and welfare of subjects is posed by the continuation of the study)
- Death
- Protocol deviation
- Pregnancy (Section 7.9)
- Other

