## 6.4. Subject Discontinuation of Study

Subjects will be free to withdraw from the study at any time should they wish to do so. Any subject may be discontinued early from the study for any of the following reasons:

- AE
- Withdrawal by subject
- Investigator decision
- Lost to follow-up (Section 6.5)
- Study termination by Sponsor
- Death
- Protocol deviation
- Pregnancy
- Other

Subjects who withdraw from the study will be encouraged to return to the site to complete an Early Termination visit Subjects who withdraw from the study will not be replaced by additional subjects.

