#### 17. STUDY TREATMENT COMPLIANCE

Compliance to study treatment will be summarized for the Safety Set. Total number of tablets expected, total number of tablets taken, total number of tablets missed, overall compliance to study treatment, frequency and percentage with overall compliance with the following categories: <85%,  $\ge85\%$  to  $\le115\%$ , and >115%. By-visit compliance will also be summarized.

Subjects with administration compliance greater than 115% and subjects who do not return any study treatment or study packaging will be asked for the reason for the overcompliance or missing study treatment. Their responses will be recorded on the Drug Accountability eCRF and will be listed.

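### For subjects who stop drug early, both SAPs end the compliance denominator at an undefined study withdrawal date rather than at the last dose, so tabulated compliance depends on the gap between the two

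*SAP*

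**What the plan says.** Main Study SAP 17.1 defines compliance as units dispensed minus units returned, divided by units prescribed. Dosing is three times daily, and the expected period runs to the evening before the final return visit. For subjects who stop drug for good before Week 12, the closing visit date "in Overall Compliance calculations will be replaced by the date of study withdrawal". LTE SAP 16.1 applies the same replacement to subjects who "permanently stop the study treatment before Week 52". Neither SAP defines the withdrawal date in its visible text.

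The protocol keeps the two events apart. Section 6.1 begins "A subject's study treatment may be discontinued early for any of the following reasons", and Section 6.4 begins "Any subject may be discontinued early from the study for any of the following reasons". The SAPs also separate them: drug discontinuation comes from the action taken on the AE page, and study discontinuation from the End of Study form (Main Study SAP 19.1.4 and 19.1.5; LTE SAP 18.1.4 and 18.1.5).

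On timing, Protocol 6.4 states: "Subjects who withdraw from the study will be encouraged to return to the site to complete an Early Termination visit". Protocol 3.10 adds: "Every effort should be made to schedule Early Termination procedures within 3 days of the last dose of study treatment".

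Main Study SAP 17 tabulates tablets expected, taken and missed, by-visit compliance, and "frequency and percentage with overall compliance with the following categories", the lowest category being under 85%. LTE SAP 16 plans the same summaries. LTE SAP 15 already takes the last dose date from the LTE End of Study form, but LTE SAP 16.1 does not use it.

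**The concern.** The rule is triggered by one event, stopping drug, and closed by another, leaving the study. The numerator stops growing at the last dose, while the denominator runs on to whatever date is programmed as withdrawal. If that date is more than one day after the last dose, days off drug are counted as missed tablets. If it is the same day as the last dose, the denominator is one day short and compliance is overstated. Two programmers could follow the same sentence and produce different tables.

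What is at stake is descriptive: overall compliance, tablets expected and missed, and the count of subjects below 85%. The population covered may not be small in the extension. LTE SAP 4.3 records that the LTE was ended early for all subjects, so every subject still on drug short of Week 52 at that point falls under the rule.

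**Working it through.** **Inputs.** Three doses a day, and an expected period ending the evening before the final return date (Main Study SAP 17.1, LTE SAP 16.1). Early Termination procedures are targeted within 3 days of the last dose (Protocol 3.10). The lag k from last dose to withdrawal is not given, so it is shown as a range from 0 to 3. The Main Study overall formula does not appear in the text available. Its structure is inferred from the per-visit formula, the worked example and the LTE overall formula.

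**1. The plan's own figures.** Expected units = 3 × (end date − first dispensing date). Main Study: 3 × (85 − 1) = 252. LTE: 3 × (387 − 1) = 1,158. Both match the SAPs.

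**2. A fully adherent early stopper.** Dispensed on Day 1, three doses every day through Day d, withdrawal dated Day d+k. Units taken = 3d. Units expected = 3(d+k−1). Compliance = d/(d+k−1).

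| Last dose Day 28, lag k | Calculation | Tabulated compliance |
|---|---|---|
| 0 | 28/27 | 103.7% |
| 1 | 28/28 | 100% |
| 2 | 28/29 | 96.6% |
| 3 | 28/30 | 93.3% |

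At k=3 the table would also show 90 − 84 = 6 missed tablets for a subject who missed none.

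**3. Other stopping days at k=3.** Day 11: 11/13 = 84.6%. Day 14: 14/16 = 87.5%. Day 56: 56/58 = 96.6%. Day 100: 100/102 = 98.0%. Falling below 85% needs d/(d+2) < 0.85, that is d < 1.70/0.15 = 11.3, so Day 11 is the latest such stop. At k=2 the condition is d/(d+1) < 0.85, and the latest such stop is Day 5.

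**4. Imperfect but acceptable dosing.** A Day 28 stopper who took 76 of 84 doses has 76/84 = 90.5%. At k=3 the rule gives 76/(3 × 30) = 76/90 = 84.4%. In general, at k=3 true compliance from 85% up to 85% × (d+2)/d is moved below 85%. That upper end is 91.1% for a Day 28 stop, 88.0% for Day 56 and 86.7% for Day 100.

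**5. The per-visit figure.** The per-visit denominator ends at the next visit date, so the interval in which dosing stops has the same problem. Taking Week 2 as Day 15 (assumed nominal), with last dose on Day 28 and the next visit on Day 31: 14 days of dosing over 31 − 15 = 16 days gives 87.5%.

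**6. Ending at last dose plus one day.** Expected units = 3 × ((d+1) − 1) = 3d, so full adherence gives 100% at every stopping day. The extra day is needed: the bare last dose date gives 28/27 = 103.7% for Day 28 and 7/6 = 116.7% for Day 7.

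**The case against.** Counting prescribed doses until formal withdrawal can be defended while drug is still prescribed. A subject who quietly stops on Day 14 and withdraws on Day 28 scores 14/27 = 51.9% under the present rule and would score 100% under the change. This stands as a real cost, and it is why the gap should be listed.

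Three days is also the outer edge of the Early Termination target, not a typical lag, and withdrawal may come before that visit. This stands too, so the k=3 figures are the upper end of the on-target range.

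The 85% figure in Protocol 5.6 ("If compliance is not between 85% and 115%, inclusive") is a trigger for counselling at named visits. It is not a limit on an early stopper's overall figure. It matters here only because the SAPs use the same cut-point as a table category.

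Three stronger readings are tempting:

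- **Withdrawal dated at the follow-up visit.** At 11 to 17 days after the last dose in the Main Study, a fully adherent Day 28 stopper would show 73.7% to 63.6%. No section ties withdrawal to follow-up, so these figures are not claimed.
- **Understated Main Study exposure.** SAP 16 takes the last dose date from an On Site Dosing Administration form, although drug is taken at home. The form's fields are not shown, and the same section has a Dosing Administration eCRF recording dose interruptions, which points away from a clinic-only form. No shortfall is claimed.
- **Damage to efficacy results.** The primary analysis uses the full analysis set without regard to compliance. The Per Protocol Set would be touched only if gross non-compliance (SAP 6.4, which names no threshold or variable) were judged from this figure.

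**Conclusion.** The point holds as a defect in a descriptive derivation. Both SAPs close the denominator on an undefined date that belongs to a different event, and the result is exact only when that date is one day after the last dose.

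Within the Early Termination target the error is modest: for a fully adherent Day 28 stopper it runs from 3.7 points too high to 6.7 points too low. It can still move subjects with acceptable dosing into the under-85% category. The effect shrinks with longer exposure, so the LTE may have many subjects under the rule but little bias in each.

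This rests on the inferred Main Study overall formula, on three doses taken on the last dosing day, and on a lag of 0 to 3 days. The documents do not give the number of early stoppers, so the number of subjects misclassified cannot be stated.

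**What to change.** In Main Study SAP 17.1 and LTE SAP 16.1, for early stoppers, end the overall denominator at last dose date plus one day. Do the same for the per-visit denominator in the interval in which dosing stops.

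In the LTE, use the End of Study last dose date already named in LTE SAP 15. In the Main Study, name one source for the last dose date, with eDiary dosing entries reconciled with drug accountability as the fallback. In either part, if the last dose date is unknown, use the withdrawal or last contact date.

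List the days between last dose and withdrawal for each early stopper, so that unreported stopping stays visible.

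For Main Study exposure, ask only that SAP 16 confirm that the On Site Dosing Administration form holds the actual last dose date.

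The cost is a wording change in two documents, a revised derivation, a short listing, and a small reconciliation step where sources disagree. The trade-off is that subjects who stopped on their own before formal withdrawal will score higher than they do now.
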